7.8.3.3 Pharmacokinetic Analysis Set

The PK analysis set will include all subjects who receive at least 1 dose of K0706 and have at least 1 measured K0706 plasma concentration at a scheduled PK time point postdose with no important protocol deviations, violations, or events thought to significantly affect the PK of the drug.

7.8.4 Pharmacokinetic Analysis

7.8.4.1 Statistical Analysis of Pharmacokinetics

Plasma concentrations and PK parameters for K0706 will be listed and summarized. Any additional PK evaluations or illustrations will be described in the SAP.

7.8.5 Efficacy Analysis

All efficacy analysis will be performed separately per Cohort (designated from Cohort A to C), and will include all subjects in the efficacy analysis set enrolled. Primary and

secondary efficacy response rates will be summarized by both point estimates and estimation of [REDACTED] confidence intervals. Detailed information for censoring rules for PFS and OS will be incorporated in the SAP. More detailed information about estimation of treatment effects, summarization of data, graphical representations, and analysis conventions will be provided in the SAP.

7.8.6 Subject Disposition

Subjects will be summarized as per the disease Cohort (i.e.: Cohorts A, B or C).

Subjects receiving treatment will be presented. Subjects receiving treatment who are found not to have fully met the eligibility criteria will be presented. On-study protocol violations will also be presented. Subjects who do not complete the required observations will be listed and evaluated separately as necessary. Study completion rates by Cohort, and reasons for study discontinuation will be summarized. Numbers of subjects enrolled in each analysis population will be presented.

7.8.7 Subject Characteristics

All baseline and demographic variables will be summarized descriptively, using [REDACTED]. The results will be presented in summary tables and by-patient listings. Baseline disease characteristics will be presented descriptively.

7.8.8 Exploratory Analysis

Continuous PD endpoints will be summarized by dose cohort and/or disease subsets or disease cohorts and scheduled visit by descriptive statistics [REDACTED]. Categorical endpoints will be summarized by proportion in each category by dose cohort and scheduled visit.

Any additional PD evaluations will be described in the SAP.

7.8.9 Safety Data Analysis

Individual and summary blood pressures, heart rate, ECG parameters and clinical laboratory data will be presented in tabular form [REDACTED] as appropriate. The data will be summarized by dose cohort and scheduled visit. Unscheduled data will not be included in the summary tables, but will be included in the listings.

For the laboratory safety data, out of range values will be flagged in the data listings and a list of clinically significantly abnormal values will be presented.

Adverse events will be tabulated and summarized according to the current version of MedDRA. AEs will be summarized according to dose and disease cohorts.

7.8.10 Data Safety Monitoring Board

A DSMB will be established for periodic review of safety data for this study. The composition and responsibilities of the DSMB will be described in detail within the DSMB Charter for this study Section 8.5.

7.9 STUDY REPORT

A clinical study report, compliant with the requirements of ICH E3, will be prepared [REDACTED]

[REDACTED]

8 REGULATORY AND ETHICAL ISSUES: PARTS B & C

8.1 Regulatory and Ethics Review and Approval

This study is to be conducted according to globally accepted standards of GCP (as defined in the ICH E6 Guideline for GCP), in agreement with the latest revision of the Declaration of Helsinki and in keeping with local regulations. Before initiation of the study, approvals from the applicable Regulatory Authority(ies) will be obtained. The Investigator must obtain approval or favorable opinion of the protocol, ICF and any advertisement for subject recruitment from the Ethics Committee complying with the applicable pertinent government regulations. The Ethics Committee will evaluate the ethical, scientific and medical appropriateness of the study.

The documents submitted will include but are not limited to the final protocol, the IB, the ethics application form, and the ICF.

The study will not commence unless the following conditions are satisfied:

An Ethics Committee has given a favorable opinion in relation to the clinical study; and
The clinical study has been authorized by the licensing authority

8.2 Subject Information and Informed Consent

Before any study-related activities are carried out such as Screening and enrolment, each prospective candidate will be given a full explanation of the study, allowed to read the approved ICF in a local language and will be provided ample time and opportunity to ask any questions that may arise. Once all questions have been answered and the Investigator is assured that the individual understands the implications of participating in the study, the subject will be asked to give consent to participate in the study by signing and personally dating the ICF. The Investigator will provide a copy of the signed and dated ICF to each subject.

The nature of the ICF will comply with the current version of the Declaration of Helsinki, the current requirements of GCP and local regulations, which ever provides the greater subject protection.

If an amendment to the protocol changes the subject participation schedule in scope or activity, or increases the potential risk to the subject, the ICF must be revised and submitted to an Ethics Committee for review and approval or favorable opinion. The revised ICF must be used to obtain consent from any subject currently enrolled in the study if he is affected by the amendment. The revised ICF must be used to obtain consent from any new subjects who are enrolled into the study after the date of the approval or favorable opinion of the amendment by the Ethics Committee.

The signed and dated declaration of informed consent will remain at the Investigator's study center, and must be safely archived by the Investigator so that the ICFs can be retrieved at any time for monitoring, auditing, and inspection purposes.

8.3 Statement of Confidentiality

The confidentiality of records that may be able to identify subjects will be protected in accordance with applicable laws, regulations, and guidelines.

A unique number will be assigned to each subject, immediately after informed consent has been obtained. This number will serve as the subject's identifier in the trial as well as in the clinical trial database. All subject data collected in the trial will be stored under the appropriate patient number. Only the Investigator will be able to link trial data to an individual subject via an identification list kept at the site. Once the trial has been completed, identifiers will be retained for as long as is required by law and by institutional regulations, and at that point will be destroyed.

To comply with ICH Guidelines for GCP and to verify compliance with this protocol, for each subject, original medical data will be accessible for the purposes of source data verification by the monitor, audits and regulatory inspections (eg, FDA, EMA, Medicines and Healthcare products Regulatory Agency, Pharmaceuticals and Medical Devices Agency), the sponsor's designated auditors, and the appropriate IRBs and IECs but patient confidentiality will be maintained. The sponsor and/or its representatives accessing the records and data will take all reasonable precautions in accordance with applicable laws, regulations, and guidelines to maintain the confidentiality of subjects' identities.

The results of studies, containing subjects' unique identifying number, will be recorded. They may be transferred to, and used in, other countries which may not afford the same level of protection that applies within the countries where this study is conducted. The purpose of any such transfer would include: to support regulatory submissions, to conduct new data analyses to publish or present the study results, or to answer questions asked by regulatory or health authorities.

Data protection and privacy regulations will be observed in capturing, forwarding, processing, and storing patient data. Subjects will be informed accordingly, and will be requested to give their consent on data handling procedures in accordance with national regulations.

8.4 Indemnity and Compensation

The Sponsor will indemnify the Investigators from all and any claims arising out of this study except for their negligence or malpractice and providing that the study is conducted according to the standards established by the protocol.

In the event that it can be demonstrated that a subject suffers any significant deterioration in health or well-being or any harmful susceptibility or toxicity as a direct result of their participation in this study then the Sponsor will agree to abide by the current FDA guidelines, as well as any local regulations that may apply, with regard to compensation payable to the subject. The amount of compensation will be calculated by reference to the level of damages commonly awarded in law for similar injuries at the time when such an injury occurred.

The Investigators declare to having insurance cover for the malpractice and/or negligence of their employees and age.

8.5 Data Safety Monitoring Board

An independent DSMB will be established to periodically review safety results of Pivotal Part C study. The DSMB will have access to study data. Based on the results of the interim review the DSMB will submit its recommendations in written form to the Sponsor who is responsible for responding to the recommendations of the DSMB and to take appropriate action. The Investigators will only be informed by the Sponsor in case of stopping the study. The DSMB may choose to request additional evaluations at any time if they feel this is warranted from the standpoint of safety.

The DSMB will act according to its own written SOP described in a charter and will prepare written minutes of its meetings. In order not to disseminate the data only the members of the DSMB and the statistician will have access to these data. The results will be sent confidentially to the DSMB by the statistician.

9 STUDY MANAGEMENT: PARTS B & C

9.1 Quality Assurance and Quality Control

In accordance with the guideline for ICH GCP, the Sponsor has responsibility for implementing and maintaining quality assurance and quality control systems, and the ultimate responsibility for the quality integrity of the study data resides with the Sponsor.

Data will be captured in a standardized format according to the study center's standard operating procedures and those procedures specified in the study documentation.

A Code of Federal Regulations Title 21, Part 11-compliant EDC system will be used for this study. The eCRFs will be produced for each subject. Where eCRFs are not possible, the source data will be captured on paper.

The Investigator will ensure the accuracy, completeness and timeliness of the data recorded for data queries and all required reports according to any instructions provided.

9.2 Protocol Adherence

The protocol must be read thoroughly and the instructions followed exactly. Any deviations should be agreed by both the Sponsor and the Investigator, with the appropriate written and approved protocol amendments made to reflect the changes agreed upon. Where the deviation occurs for the well-being of the subject, the Sponsor must be informed of the action agreed upon.

9.3 Documents Necessary for Initiation of Study

For the documents necessary for initiation of study please refer to applicable regulatory and GCP requirements for the country.

9.4 Study Monitoring

This study will be monitored in accordance with the ICH GCP. The clinical monitor, whether an employee of the Sponsor or its designated representative, has the obligation to follow this study closely. In doing so, the clinical monitor will visit the clinical study center at periodic intervals, in addition to maintaining necessary telephone and letter contact. The clinical monitor will monitor current personal knowledge of the study through observation, review of study records and source documentation and discussion of the conduct of the study with the Investigator and study center staff. Quality assurance auditors, whether employees of the Sponsor or its designated representative, may evaluate the conduct of the study by the study center at any time during or after the study to ensure the validity and integrity of the study data. These parties must have access to all study reports and source documentation, regardless of location and format.

Upon completion of the study, the clinical monitor will arrange for a final review of the study files, after which the files should be secured for the appropriate time. The Investigator, or appointed delegate, will meet with the monitor during the on-site visits and will co-operate in providing the documents for inspection and respond to inquiries. In addition, the Investigator will permit inspection of the study files by authorized representatives of the Sponsor or the regulatory agencies.

The Investigator will allow study-related monitoring audits, Ethics Committee and regulatory inspections allowing direct access to study-related source data/documents.

9.5 Study Closure

The Investigator reserves the right to terminate the study in the interest of subject welfare.

The Sponsor may terminate the study at any time.

Premature termination of the study by any party will be governed under the terms of the contract between the parties and the prevailing safety and well-being of subjects.

The end of the study is defined as 'the last visit of the last subject in the study'. This would be the last follow-up of the last subject, however, the study may be concluded earlier if required by the Sponsor.

9.6 Study Record Retention

The Sponsor and the Principal Investigator shall ensure that the documents contained, or which have been contained, in the Trial Master File are retained for at least 15 years after the conclusion of the study and that during that period are:

Readily available to the licensing authority on request; and Complete and legible.

All data derived from the study will remain the property of SPARC. The study will be the subject of a final clinical study report compiled by, or by order of SPARC.

All correspondence (e.g., with the Sponsor, Ethics Committee) relating to this study should be kept in the appropriate file folders.

Records of subjects source documents, eCRF's, IMP inventory, pertaining to the study must be kept on file. Records must be retained according to the current ICH Guidelines on GCP.

The Sponsor and Principal Investigator shall ensure that the medical files of study subjects are retained for at least 15 years after the conclusion of the study. The Sponsor shall appoint named individuals within his organization to be responsible for archiving the documents which are, or have been, contained in the Trial Master File. Access to those documents shall be restricted to those appointed individuals. If there is transfer of ownership of data or documents connected with the clinical study:

The Sponsor shall record the transfer; and the new owner shall be responsible for data retention and archiving

If the Investigator moves, withdraws from an investigation or retires, the responsibility for maintaining the records may be transferred to another person who will accept responsibility. Notice of transfer must be made to and agreed by the Sponsor.

[figure not shown]
9.7 Publication Policy

[figure not shown]
After completion of the study, the Investigator may prepare a joint publication with the Sponsor. The Investigator must undertake not to submit any part of the individual data from this protocol for publication without prior consent of the Sponsor at a mutually agreed time.

[figure not shown]

13 APPENDIX

13.1 APPENDIX I

CRITERIA FOR RESPONSE

Haematological response

Major haematological response (MaHR) is inclusive of complete haematological response (CHR) and/or no evidence of leukemia (NEL).

For subjects who enter the study in MaHR response, the criteria for evaluating response is: Maintenance of MaHR for upto 12 weeks after initiation of study treatment.

These criteria are adapted from Talpaz et al., 2006, O'Brien et al., 2003, and Kantarjian et al., 2010.

| Haematological response criteria for Subjects with CML-AP and CML-BP and Ph+ ALL | |
|--|---|
| CHR | 
 • White blood cells (WBCs) \leq Institutional upper limit of normal • $ANC \geq 1000/mm^3$ • Platelets $\geq 100,000/m^3$ • No blasts or promyelocytes in peripheral blood • $< 5\%$ basophils on differential • $< 5\%$ myelocytes and metamyelocytes on peripheral blood • No extra-medullary involvement (no hepatomegaly and/or splenomegaly) |
| NEL | 
White blood cells (WBCs) \leq Institutional upper limit of normal
 
No blasts or promyelocytes in peripheral blood
 
$< 5\%$ basophils on differential
 
$< 5\%$ myelocytes and metamyelocytes on peripheral blood
 
No extra-medullary involvement (no hepatomegaly and/or splenomegaly)
 
At least one of the following
 
 • $20,000/mm^3 \leq Platelets \leq 100,000/mm^3$ • $500/mm^3 \leq ANC \leq 1000/mm^3$ |

| Complete haematological response (CHR) for Subjects with CML-CP | |
|---|--|
| CHR | 
Platelets $< 450 \times 10^9/mm^3$
 
White blood cells (WBCs) \leq Institutional upper limit of normal
 
No blasts or promyelocytes in peripheral blood
 
$< 5\%$ basophils on differential
 |

| | |
|--|---|
| | < 5 % myelocytes and metamyelocytes on peripheral blood No extra-medullary involvement (no hepatomegaly and/or splenomegaly) |
|--|---|

Cytogenetic response:

Criteria for Cytogenetic response have been derived from Kantarjian et al, 2006, Talpaz et al, 2006 and National Comprehensive Cancer Network (NCCN), Clinical practice guidelines (2018).

At least 20 metaphase should be evaluated. If fewer metaphases are reported, absolute percentage values should be reported. Peripheral blood cells must not be used.

| Major Response | Cytogenetic Response | Complete (CCyR) | No Ph+ Cells |
|------------------|----------------------|-------------------------|--------------------|
| | | Partial Response (PCyR) | 1-35 % Ph+ Cells |
| Minor Response | | | 36-65 % Ph+ Cells |
| Minimal Response | | | 66-95 % Ph+ Cells |
| No Response | | | 96-100 % Ph+ Cells |

Under limited bone marrow aspirate availability precluding cytogenetic evaluation by Giemsa staining, FISH assay for evaluation of Ph+ Cells will be performed. A CcyR is reported for FISH when No Ph+ cells* are observed or fewer than 1 out of 200 nuclei BCR-ABL1-positive by FISH.

Major Molecular Response:

A major molecular response (MMR), is defined as a ratio of reverse transcribed transcript of BCR-ABL to ABL ≤ 0.1 % on the international scale (IS) (equivalent to 3 log reduction in transcript) (Baccarani et al., 2009).

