7.3.1.4 Trial End points

7.3.1.4.1 Primary Endpoints

- Cohort A: For CML subjects in CP at study entry: major cytogenetic response (MCyR), defined as complete cytogenetic response (CCyR) or partial cytogenetic response (PCyR).
(CP subjects in CCyR are not eligible for this study)
- Cohort B: For CML subjects in AP at study entry: major hematologic response (MaHR), defined as complete hematologic response (CHR) or no evidence of leukemia (NEL). (AP subjects in MaHR are not eligible for this study)
- Cohort C: For CML subjects in BP at study entry: MaHR, consisting of CHR or NEL. (BP subjects in MaHR are not eligible for this study)

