7.3.2.2 Classification of CML subjects

Subjects will be classified as per the NCCN guidelines for Chronic Myeloid Leukaemia¹³ as follows

Table 7-2 Classification of Subjects with CML

| CML Phase | Criteria |
|-------------------|--|
| Chronic Phase | $< 15\%$ blasts in peripheral blood or bone marrow and $< 20\%$ basophils in peripheral blood and $< 30\%$ (blasts + promyelocytes) in peripheral blood or bone marrow and $> 100 \times 10^9$ platelets/L in peripheral blood and No extra-medullary disease |
| Accelerated Phase | $\geq 15 - < 30\%$ blasts in peripheral blood or bone marrow or $\geq 20\%$ basophils in peripheral blood or bone marrow or $\geq 30\%$ (blasts + promyelocytes) in peripheral blood or bone marrow (but $< 30\%$ blasts) or $\leq 100 \times 10^9$ platelets/L in peripheral blood unrelated to therapy or Additional clonal cytogenetic abnormalities in Ph+ cells |
| Blast Crisis | $\geq 30\%$ blasts in peripheral blood, bone marrow or both or Extra-medullary disease |

Note: For subjects wherein rapid disease progression is observed (beyond the aforementioned criteria) and subject safety is a concern, the subject can be discontinued at Investigator's discretion in consultation with Sponsor or Sponsor nominated CRO's medical monitor.

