pathology laboratory and/or pathologist performing the cytogenetic and fluorescence in situ hybridization analysis is blinded to treatment information and is trained in performing the procedure under appropriate aseptic conditions. Documentation of subject's treatment information cannot be contained in any request forms or directives for sample processing.

Fluorescence in situ hybridization analysis (performed on bone marrow) will also be used to confirm presence of BCR-ABL fusion product in case of subjects who have achieved complete cytogenetic response with study drug or have minimum residual disease.

Bone marrow cell differential will also be used to determine the blast and immature myeloid counts and cellularity if required.

Physical examination will be used to assess hepatic and spleen involvement.

To understand the exploratory objectives:

In the study, serum, blood, and bone marrow-based samples will be collected at specified time points to determine the following:

- BCR-ABL mutation profile at screening
- BCR-ABL mutation profile at progression (should it occur)

Samples for BCR-ABL mutation profiles will be performed during Screening and at progression if observed. Additional efficacy parameters may be evaluated and will be detailed in the statistical analysis plan.

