7.8.1 Primary and Secondary Target Variables

Primary Endpoints

- Cohort A: For CML subjects in CP at study entry: major cytogenetic response (MCyR), defined as complete cytogenetic response (CCyR) or partial cytogenetic response (PCyR). (CP subjects in CCyR are not eligible for this study)
For subjects entering the study in PCyR, achieving CCyR on the study drug will be considered as MCyR.
- Cohort B: For CML subjects in AP at study entry: major hematologic response (MaHR), defined as complete hematologic response (CHR) or no evidence of leukemia (NEL). (AP subjects in MaHR are not eligible for this study)
- Cohort C : For CML subjects in BP : MaHR, consisting of CHR
Or NEL. (BP subjects in MaHR are not eligible for this study)

Secondary Endpoints

- In subjects with CML-CP
 - Hematological responses: Proportion of subjects who develop complete hematological response
 - Cytogenetic responses: Proportion of subjects who develop CCyR
 - Molecular responses: Proportion of subjects who achieve MMR
- In subjects with CML-AP or CML-BP

- Cytogenetic responses: Proportion of subjects who achieve CCyR or PCyR,
- Molecular responses: Proportion of subjects who achieve MMR
- In all subjects: Safety and tolerability in terms of incidence and severity of treatment emergent AEs
- In all subjects: Time to response, duration of response, progression free survival and overall survival

Table 7-13 Efficacy Assessment of Primary End points

| | Cohort A | | Cohort B and C ^a |
|-------------------------------|---|--|---|
| Primary endpoint will include | Subjects entering the study with less than PCyR | Unconfirmed MCyR: That is detection of a complete or partial cytogenetic response on a single bone marrow aspirate will qualify as a response for determination of efficacy. | Confirmed MaHR: This includes demonstration of CHR or NEL confirmed by 2 hematological assessments performed at least 4 weeks apart. The hematological assessments will include a peripheral blood CBC and differential to qualify as a response. |
| | Subjects entering the study with PCyR | Unconfirmed CCyR: That is detection of Complete cytogenetic response on a single bone marrow aspirate will qualify as a response for determination of efficacy. | |

a: Criteria for responses are included in Appendix 1

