10 MEDICATIONS

Prior, concomitant, and post-therapies will be coded using the latest available version of the Anatomical Therapeutic Chemical (ATC) classification text from the World Health Organization Drug Dictionary (WHO DD) and summarized using safety analysis set. Surgical and medical procedures will be coded by primary system organ class (SOC) and preferred term (PT) according to MedDRA coding dictionary.

Prior therapy:

Prior therapies are therapies which started and stopped before the first dose of Vodobatinib. Any changes to prior medications (dose, regimen, etc.) during the study will be considered a new concomitant medication.

The number and percentage of subjects who received any prior including anti-neoplastic medications will be summarized by the dose group for the safety analysis set. The number and percentage of subjects who received any prior including anti-leukemic medications will be summarized by the dose group for the safety analysis set. The prior medications will be summarized for the lowest anatomical therapeutic classification (ATC) class and preferred name.

Concomitant therapies:

Concomitant therapies are defined as all interventions (medications and procedures) other than the study treatment administered to a subject coinciding with the study treatment period. Concomitant therapies include medications and medical procedures starting on or after the first dose of study treatment or starting prior to the first dose of study treatment and continuing after the first dose of study treatment. Concomitant medication will be summarized by the lowest ATC class and preferred name using frequency counts and percentages. Surgical and medical procedures will be summarized by SOC and PT. A listing will also be provided.

[REDACTED]

[REDACTED]

[REDACTED]

[REDACTED]

Hematological Response:

Hematological response is a normalization of the blood counts, particularly WBC counts and is evaluated by peripheral blood assessments and clinical assessments of extramedullary disease.

[REDACTED]

[REDACTED]

[REDACTED]

[REDACTED]

[REDACTED]

[REDACTED]

[REDACTED]

[REDACTED]

[REDACTED]

[REDACTED]

Cytogenetic Response:

Cytogenetic response is assessed by the ratio of number of Ph+ cells seen to the number of cells analyzed on Karyotyping done by the central laboratory. In cases where karyotyping was not performed then the central laboratory florescence in situ hybridization (FISH) results will be

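### CHR and NEL for CML-AP/BP set no marrow-blast limit, so a confirmed MaHR can coexist with AP or BP by Table 7-2; separately, NEL bounds only one of ANC and platelets

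*Protocol*

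**What the plan says.** Protocol Sections 7.3.1.4.1 and 7.8.1 make MaHR the primary endpoint of Cohorts B (AP) and C (BP). For Cohort C the wording is "For CML subjects in BP at study entry: MaHR, consisting of CHR or NEL", and Cohort B is parallel. Both sections add that AP and BP subjects already in MaHR are not eligible.

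Appendix I (Section 13.1) defines both components for AP and BP. CHR and NEL share a WBC ceiling, limits on basophils and on myelocytes plus metamyelocytes, absence of extramedullary involvement, and this blast criterion: "No blasts or promyelocytes in peripheral blood". CHR also needs ANC of at least 1000 and platelets of at least 100,000. NEL instead needs "At least one of the following": platelets 20,000 to 100,000, or ANC 500 to 1000 (all per mm3). Neither definition mentions marrow blasts.

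Table 7-13 (Section 7.8.1) asks for two assessments at least 4 weeks apart: "The hematological assessments will include a peripheral blood CBC and differential to qualify as a response". Its footnote sends the reader to Appendix I for the criteria. The SAP's Hematological Response paragraph says that response "is evaluated by peripheral blood assessments and clinical assessments of extramedullary disease"; the lines after it are redacted.

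Marrow blasts count elsewhere. Table 7-2 (Section 7.3.2.2) defines blast crisis as at least 30% "blasts in peripheral blood, bone marrow or both", or extramedullary disease, and lets AP be met at 15 to <30% in blood or marrow. The progression criteria (Table 7-3) also refer to blasts in blood or marrow. Section 7.7.2 names the marrow differential among the response tools, then says: "Bone marrow cell differential will also be used to determine the blast and immature myeloid counts and cellularity if required". It gives no threshold and no link to MaHR.

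**The concern.** Phase at entry and progression are judged with the marrow; response is judged without it. A subject can enter Cohort C because of marrow blasts, clear the blood, keep a marrow in the blast range, and be scored a success on the cohort's only primary endpoint.

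The NEL wording raises a different problem. Leaving one count unbounded lets severe cytopenia qualify as absence of leukemia.

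The entry rule mirrors the first problem. A subject who is AP or BP only by marrow, with blood that already meets CHR or NEL, belongs in the cohort by Table 7-2 but is in MaHR by Appendix I, and so is ineligible. Appendix I also gives a response rule for subjects who enter in MaHR (maintenance for up to 12 weeks), although Sections 7.3.1.4.1 and 7.8.1 bar such subjects. That rule may be meant for Part B, but the appendix does not say so.

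At stake is the meaning of the response rate in two of the three Part C cohorts.

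**Working it through.** **Plan's own figure.** The MaHR benchmark in Section 7.8.2 reproduces: 5/24 = 20.8%. Sample size, null and alternative rates, alpha and power for Cohorts B and C are redacted, so no design figure can be re-derived.

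**Rules side by side.** The Appendix I and Table 7-2 rules were applied to hypothetical subjects. All have WBC within the normal limit, no circulating blasts or promyelocytes, and basophils and myelocytes/metamyelocytes below 5%. None has extramedullary disease except in row 4. The same findings are taken to hold at both confirmatory assessments.

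| | Marrow blasts | ANC /mm3 | Platelets /mm3 | Appendix I | Phase by blasts or extramedullary disease, Table 7-2 |
|---|---|---|---|---|---|
| 1 | 40% | 2000 | 150,000 | CHR | Blast crisis |
| 2 | 40% | 2000 | 50,000 | NEL | Blast crisis |
| 3 | 20% | 2000 | 150,000 | CHR | AP |
| 4 | 40%, with extramedullary disease | 2000 | 150,000 | No response | Blast crisis |
| 5 | 2% | 100 | 40,000 | NEL | Neither |
| 6 | 2% | 700 | 5,000 | NEL | Neither |
| 7 | 2% | 100 | 150,000 | No response | Neither |
| 8 | 2% | 2000 | 5,000 | No response | Neither |

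Rows 1 to 3 show the contradiction, and it comes only through marrow blasts. Row 4 shows that the extramedullary route to blast crisis is closed.

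Rows 5 to 8 show the NEL fault. Against row 7, row 5 has the same ANC and fewer platelets, yet it becomes a response. Against row 8, row 6 has the same platelets and a lower ANC, yet it becomes a response. A worse count should not turn a non-response into a response.

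**Effect of each repair.** Requiring ANC of at least 500 and platelets of at least 20,000 for NEL removes rows 5 and 6 but leaves row 2. Refusing a MaHR when marrow blasts are still 15% or more removes rows 1 to 3 but leaves rows 5 and 6. Both repairs are needed.

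**Direction.** Every responder under the repaired rules is also a responder under the present ones. For a given set of subjects the present rate can therefore only be equal or higher.

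**Size.** The documents do not give the frequency. With an assumed n of 24, the size of the benchmark series, one case is 1/24 = 4.2 points and two are 2/24 = 8.3 points.

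As an illustration only, assume one-sided alpha 0.025, n = 20, 30 or 40, and a null rate p0 of 5% or 10%. Let r be the smallest count with P(X ≥ r | n, p0) ≤ 0.025, and let a further share f of subjects score only because marrow is ignored. The chance of reaching r is P(X ≥ r | n, p0 + f):

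- f = 0: 0.8% to 1.6%
- f = 2 points: 2.2% to 5.8%
- f = 5 points: 6.7% to 20.6%

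These figures show sensitivity. They do not estimate what will happen in this trial.

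**The case against.** Several points on the other side narrow the concern.

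- **Confirmation.** One clear visit is not a response; Table 7-13 requires two at least 4 weeks apart. A reader might infer that early hydroxyurea manufactures responses, but Section 7.4.6.2 has it stopped by the end of week 3 in AP and BP. That mechanism is weak.
- **Progression rules.** Table 7-3 counts rising marrow blasts in BP as progression, and in AP it counts blasts that do not fall over 4 weeks, or confirmed BP. The gap is mainly BP with stable or partly reduced marrow blasts. No visible rule voids a MaHR already scored.
- **Stronger readings.** A reader might say the endpoint rests on peripheral blood alone, or that the loose count rule lets blast crisis through. Neither is right. Extramedullary disease is also assessed, CHR has floors on both counts, and no ANC or platelet value makes a subject blast crisis under Table 7-2.
- **A real change.** If subjects in MaHR are excluded at entry, a later responder did change on study. That is true, but a change in blood is not the disease status that Table 7-2 describes.
- **Unseen text.** SAP criteria are partly redacted, Section 7.5.2.4 also points to an Operations Manual, one list in Section 7.7.2 is partly redacted, and Table 7-13 does not say that blood counts are the only assessment. A marrow rule could sit in any of these. However, the Table 7-13 footnote names Appendix I as the source of the criteria, and its CHR and NEL tables are visible. A marrow rule elsewhere would have to be reconciled with it.
- **Comparability.** The response criteria are adapted from publications, and it is unknown whether those or the 5/24 benchmark used a marrow limit. This stands, and the fix allows for it.

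**Conclusion.** The concern holds for the visible text, in two separate parts. First, CHR and NEL for AP and BP have no marrow-blast limit, so a subject with clear blood confirmed at least 4 weeks apart and marrow blasts in the AP or BP range is a MaHR responder while still in that phase by Table 7-2. Second, NEL leaves one of ANC and platelets unbounded, so rows 5 and 6 of the table count as responses. Both are stated rules giving a wrong result on the sole primary endpoint of two cohorts, and should be corrected before the primary analysis.

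The direction is upward. The amount is unknown: 4.2 points per subject holds only at the assumed n of 24. A reader might infer that the reported rate will be materially inflated; the documents do not support that, because nothing shows how often such cases occur. The conclusion also assumes that no marrow rule sits in the redacted SAP lines or the Operations Manual.

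**What to change.** 1. **NEL.** Reword as ANC ≥500/mm3 and platelets ≥20,000/mm3, with at least one below its CHR limit. This changes wording only.
2. **Marrow.** Reconcile Appendix I and Table 7-13 with Table 7-2: a MaHR does not count if the marrow differential from the nearest already scheduled aspirate still meets the Table 7-2 blast criteria for AP or BP. The documents give no stricter marrow limit; if one is wanted, it should come from the source criteria the sponsor adapted. Report separately any MaHR with no marrow differential available. Show the blood-only rate as a sensitivity analysis, which keeps the comparison with 5/24.
3. **Entry.** Apply the same definition to the exclusion of subjects in MaHR, and reconcile that exclusion with the Appendix I rule for subjects who enter in MaHR.
4. Carry the same text into the SAP criteria.

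**Cost.** A protocol amendment and SAP wording. Aspirates are already needed for the secondary cytogenetic endpoints in AP and BP (Sections 7.3.1.4.2 and 7.5.2.2), but the marrow differential moves from use when required to routine use on them. The aspirate schedule is not visible, so the gap between a blood response and the nearest marrow should be checked. The MaHR rate may be slightly lower, and some responses will be established later.
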